Study Protocol – Version 5, March 30, 2023

NCT05503823

Project Title: Investigating Transcranial Alternating Current Stimulation (tACS) Preconditioning Effects on Resting and Active Motor Threshold

1. Summary of the Project

Transcranial Magnetic Stimulation (TMS) is a non-invasive brain stimulation technique which uses a large and rapidly changing magnetic field pulse for stimulation. Exposure to TMS has been associated with the improvement of the brain's plasticity and memory loss [1]. These after-effects of TMS are temporal and short-term. However, repetitive sessions of preconditioning the brain before TMS has the potential to extend the duration of these after-effects while also reducing the amount of exposure necessary for observable results. The proposed study focuses on providing some insight on the effects of priming the brain via Transcranial Alternating Current Stimulation (tACS) and Transcranial Random Noise Stimulation (tRNS) before applying TMS.

In this study, single pulse TMS is applied over the primary motor cortex, specifically for the hand area to find the resting and active motor thresholds. The Resting Motor Threshold (RMT) is the lowest intensity to produce involuntary hand twitches while the hand is at a relaxed position or when the motor evoked potential has a peak-to-peak amplitude of greater than $50\mu\text{V}$ for 5 of 10 trials [2][3]. The active motor threshold (AMT) is similarly the lowest intensity at which the participant shows involuntary hand twitches, but this time while the hand is contracted. AMT is also measured similarly as the lowest intensity at which the motor evoked potential has a peak-to-peak amplitude of greater than $100\mu\text{V}$ for 5 of 10 trials [4][5]. The electromyography (EMG) of the First Dorsal Interosseous muscle (FDI) is recorded before the application of tACS as a baseline for both RMT and AMT. Then the tACS/tRNS is applied at 40Hz for 10 minutes with the active electrode over the exact location of the TMS application (the hand area of the primary motor cortex) and the reference over the right supraorbital area. Then the EMG is recorded immediately after tACS/tRNS, 30 minutes after, and 1 hour after exposure to tACS/tRNS. These recordings are done both in resting and active states of the muscle. The objective is to observe a change in the motor evoked potentials (MEPs) after exposure to tACS or tRNS and analyze the time of the sustained MEP change.

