The proposed study will be tested on 50 cognitively healthy participants from a diverse age group (18-95).

An increase in the peak-to-peak value of MEP post-tACS or post-tRNS could prove to indicate as a new technique to lower the RMT, resulting in lower intensity exposure to TMS. This will be helpful when TMS is used for treatments such as depression disorders. The goal of this study is to eventually find a preconditioning technique to increase the duration of TMS sessions to help in treatment of initial stages of Alzheimer's disease.

2. Background

Previous studies have investigated preconditioning the brain through electrical stimulation of the brain mainly using direct current application [6][7]. These studies show promising improvement of the motor evoked potential (MEP) when transcranial electric stimulation (tES)

techniques such as tDCS (transcranial direct current stimulation) are applied before a session of TMS [6][7]. This study attempts to extend the previous findings by investigating the effects of alternating current and random noise stimulations on the brain known as tACS and tRNS respectively.

tDCS

tDCS is electrical stimulation of the brain using direct current. The study by Lang et al [6] shows a prominent increase of motor evoked potential peak-to-peak amplitude caused by TMS after stimulation of the brain with tDCS over the motor cortex. This study concludes that preconditioning the brain with tDCS effectively improves the cortical plasticity during rapid TMS while also controlling the direction of TMS induced after-effects by changing the placement of the cathode and anode during application of electrical stimulation [6].

A second study conducted by Cosentino et al [7] also investigates the effects of priming the brain using tDCS in a similar setting as the previous study. Contrary to the previous study, this study shows that neither cathodal nor anodal stimulation caused a higher MEP than the baseline [7].

tACS

tACS is electrical stimulation of the brain using alternating current. This stimulation is bipolar therefore, it is not expected to see any difference between the cathodal and anodal after-effects of the priming. In this study we will extend the previous studies to investigate the effects of pre-conditioning the brain using tACS.

tRNS

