Once the minimum intensity is recorded for the RMT, the participant gets a 10-minute break from the stimulation. During this time, the RA will measure the blood pressure and oxygen level and connect the electrodes over the FDI muscle of the right hand to record EMG and prepare the participant for the TMS session. During the first TMS session, 10 single pulses are applied to the participant over the hotspot recorded by the coordinating camera. The resting EMG of the corresponding muscle in a relaxed position will be recorded for further investigation under the participant code name. Immediately after, the participant will be asked to gently hold the arm rest of the chair and the active EMG will be recorded over 10 single pulses of TMS.

The participant will be given a 5-minute break, during which the RA place the tACS active electrode on the hotspot marked by the coordinating camera and the reference on the contralateral motor cortex. When the electrodes are all set up, tACS will be applied gradually from lower current intensity to higher for 1 minute to allow the participant to adjust to the current. The current is applied at 40 Hz frequency for the duration of 10 minutes. Immediately after the application of tACS the participant's resting and active EMG will be recorded similar to the pre-tACS procedure, with 10 pulses of TMS for each of the resting and active experiments.

Also, the blood pressure and oxygen level will be remeasured. A similar procedure will be followed to record the resting and active EMG after 30 minutes and after 1 hour from the initial application of tACS.

During the second session, the participant will be monitored by the exclusion questionnaire. If the participant passes the criteria, the RMT will be measured again and a similar procedure to the first session will be followed while tRNS is used instead of tACS. The second session can begin after 4 hours following the first session and may occur on a separate day depending on the participant's availability.

Each of these procedures will be applied once on each participant and the experiment for each participant will be done after one or two visits to the laboratory.

Data collection for the study will take place for a period of one year.

All the data will be deleted and destroyed 3 years after completion of the study.

9. Deception

There is no deception in this study.

10. Feedback/Debriefing

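### The title and Sections 1 and 3 name motor-threshold outcomes, but Section 8 determines no threshold after stimulation and never determines AMT

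*Combined protocol and SAP*

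**What the plan says.** The title announces "Preconditioning Effects on Resting and Active Motor Threshold". Section 1 says single-pulse TMS is applied "specifically for the hand area to find the resting and active motor thresholds". It defines RMT as a lowest intensity: RMT "is the lowest intensity to produce involuntary hand twitches while the hand is at a relaxed position", or alternatively the intensity at which the MEP exceeds 50 µV in 5 of 10 trials. It adds that "AMT is also measured similarly as the lowest intensity at which the motor evoked potential has a peak-to-peak amplitude of greater than" 100 µV, again in 5 of 10. The EMG "is recorded before the application of tACS as a baseline for both RMT and AMT".

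The sentence that states the aim is different: "The objective is to observe a change in the motor evoked potentials (MEPs) after exposure to tACS or tRNS". Later in Section 1, a rise in MEP amplitude after stimulation "could prove to indicate as a new technique to lower the RMT, resulting in lower intensity exposure to TMS".

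Section 3 gives the measurement of RMT as the purpose of TMS and lists four times, three of them after stimulation. Its TMS parameter table gives device and location, but no intensity.

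Section 6 compares MEP amplitude at a constant TMS intensity and takes a noticeable rise to suggest that priming has lowered the threshold.

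Section 8 describes a search for RMT before stimulation, by 1% decrements to the lowest intensity with a visible twitch, and repeats it before tRNS in the second session. After stimulation, the resting and active EMG "will be recorded similar to the pre-tACS procedure, with 10 pulses of TMS for each of the resting and active experiments". The 30-minute and 1-hour recordings follow the same pattern.

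**The concern.** By the protocol's own definitions a threshold is a lowest intensity, so finding one means varying the intensity. After stimulation Section 8 varies nothing; it gives fixed blocks of 10 pulses. Followed as written, the study would lack the post-stimulation RMTs that Section 3 lists and the AMT that the title names. Section 6 would then fill the gap by reading a threshold reduction from MEP amplitude.

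The practical benefit hoped for in Section 1, lower TMS intensity through a lower RMT, depends on how far RMT falls. A report under the present title could state a threshold effect that was never measured.

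The unstated pulse intensity makes this worse. The level decides whether a block carries any information about threshold, and it is also part of the definition of the MEP outcome.

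**Working it through.** No power or sample-size formula applies. The check is a count and a comparison of sections.

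**The plan's own figure.** Section 3 speaks of eight TMS applications. This is reproduced as 4 times x 2 muscle states = 8 per session, or as 4 times x 2 sessions = 8 if only resting blocks are counted. On the first count, Section 8 gives 8 x 10 = 80 recording pulses per session and 2 x 80 = 160 over both sessions.

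**What is named against what is obtained** (left hemisphere, where the stimulation and the right-hand EMG are described):

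| Quantity | Named in | Obtained under Section 8 |
|---|---|---|
| RMT before stimulation | Title, Sections 1 and 3 | Yes, searched in each session |
| RMT immediately, 30 minutes and 1 hour after | Section 3 list | No; 10 resting pulses at each time |
| AMT, any time | Title, Section 1; mentioned in the Section 3 position-sensor text | No search; 10 active pulses at each time |
| MEP change | Section 1 objective, Section 6 | Yes, at an unstated intensity |
| cSP | Section 6 | Yes, from the active blocks |

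**Counts.** Post-stimulation RMTs listed: 3 times x 2 sessions = 6; searches described: 0. Active recording occasions: 4 times x 2 sessions = 8; AMT searches described: 0. Section 8 also searches for RMT on the right hemisphere at baseline, with no described follow-up.

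**What a fixed block can say about threshold.** Let all pulses be given at one intensity I. Scoring the Section 1 criterion (more than 50 µV at rest, or more than 100 µV when active, in 5 of 10) gives a yes or a no at I.

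- Yes places the threshold at or below I; no places it above I.
- No before stimulation and yes afterwards points to a fall across I. That is a direction without a size.
- The same answer before and after says nothing about a change on that side of I.

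A block is therefore informative about direction only if I lies near the threshold, and it never gives the size. This holds for RMT and AMT alike.

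**Is I known?** Section 6 says only that it is constant. Neither the Section 3 table nor the Section 8 narrative gives it as a percentage of RMT, of AMT or of stimulator output, or as a target MEP size. Nothing says whether resting and active blocks share it, or whether the second session keeps the intensity of the first.

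**The case against.** The strongest reply is that this is largely labelling. The only stated objective is MEP change, and Section 8 measures it. Section 1 calls the EMG a baseline for both thresholds, so RMT and AMT may simply be names for resting and active recordings. Section 6 says the rise suggests a lower threshold, not that it proves one. Much of this stands, and it is why the main remedy is wording. It does not remove the conflict: Section 1 defines both thresholds as lowest intensities, and Section 3 says RMT is measured at the three later times.

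Some readings go further than the documents allow, in both directions:

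- *The study loses its objective.* It does not; MEP change and cSP remain estimable.
- *Nothing can be learned about AMT.* Too strong. The 100 µV criterion could show direction in an active block, on the same condition as for RMT.
- *The post-stimulation procedure includes a search, because it is modelled on the pre-stimulation one.* The sentence concerns EMG recording with 10 pulses per state, and Section 6 holds the intensity constant.
- *The second-session RMT is a follow-up to tACS.* It comes at least 4 hours after the first session, at none of the listed times, and before tRNS.
- *The pulses are plainly given at RMT.* This is natural, since the blocks follow the RMT search, but it is not stated and would leave the active blocks without an AMT reference.
- *A larger MEP can never be told apart from a steeper response curve.* How far the two separate depends on the pulse level, which is unknown, and the documents give no amplitude model to test it.
- *The twitch rule in Section 8 is an error.* Section 1 permits it.

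**Conclusion.** The point holds in this form. Section 8 provides 0 of the 6 post-stimulation left-hemisphere RMTs listed in Section 3, and no AMT at any time. MEP change and cSP can be estimated; the size of an RMT or AMT change cannot. A block can show at most the direction of a threshold change, and whether it can is undetermined because the pulse intensity is not stated. Section 6's inference to a reduced threshold is therefore indirect.

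The mismatch between the named thresholds and the described procedure is wrong as written and should be corrected. The missing intensity, taken alone, would be an unspecified detail. The conclusion rests on the text and on the protocol's own definition of a threshold; it needs no assumed response curve, threshold value or pulse timing.

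**What to change.** Reconcile the title and Sections 1, 3, 6 and 8:

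- Name MEP peak-to-peak amplitude, at one constant intensity stated by the sponsor, and cSP as the outcomes.
- State whether resting and active blocks, and both sessions, share that intensity.
- Call the Section 3 measurements resting and active EMG recordings.
- Reword Section 6 so that a larger MEP is an indirect indicator of excitability and not a finding that the threshold fell. The sentence need not be deleted.

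The cost is wording, one stated level and a narrower claim with no threshold effect. No pulses or visits are added.

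If the sponsor wants threshold outcomes instead, Section 8 must describe RMT and AMT determination at the listed times. That adds 3 RMT and 4 AMT determinations, so 7 per session, and the fit must be checked. The two breaks and the hour from the start of tACS take 10 + 5 + 60 = 75 of the 120 minutes implied by the two-hour session in Section 7. The other 45 minutes must already hold the remaining work, which in the first session includes consent, MoCA, the questionnaire, scalp measurement and the RMT searches on both sides. The sponsor would also need to check that two determinations plus the recordings still count as immediately after stimulation. The documents give no time per pulse, so feasibility cannot be settled from them. This is a larger change and the sponsor's choice.
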